**NOTES:**

1. In the event of subject death during the conduct of the study, efforts should be made to perform an autopsy.
2. Sensations or side effects that occur during the programming session should not be reported as AEs. However, undesired sensations or side effects caused by the final programming parameters (including active contact, pulse width, frequency, and amplitude) that persist or occur after the completion of the programming should be reported as AEs.
3. Lack of efficacy/decreased therapeutic response should not be reported as AEs. Clinical sequelae, other than pain, that occur as a result of lack of efficacy/decreased therapeutic response should be reported as AEs
4. Clinically significant worsening of the pattern of intensity or distribution of Baseline pain symptoms should be reported as an AE.
5. Device deficiencies, including, but not limited to device/lead migrations, which are not associated with an adverse clinical outcome should only be reported as device deficiencies. However, if a device deficiency precipitates an AE, the AE should be reported in the Adverse Event eCRF and the device deficiency should be documented in the Device Deficiency eCRF.
6. If device implantation is unsuccessful, the subject will be followed for 2 weeks post implantation attempt to assess for procedure related adverse events. If the device is explanted, the subject will be followed for 2 weeks post explant to assess for related adverse events.

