### 6.6. *Safety Parameters*

Safety parameters include the rates of occurrence of all device hardware, device stimulation and procedure related non-serious adverse events, all serious adverse events, and unanticipated adverse events through the end of the study.

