## 17. Safety Reporting

### 17.1. Reportable Events by investigational site to Boston Scientific

It is the responsibility of the investigator to assess and report to BSC any event which occurs in any of following categories:

- All Serious Adverse Events
- All Device Deficiencies
- Unanticipated Adverse Device Effects
- New findings/updates in relation to already reported events
- Device-hardware, device-stimulation, and procedure related non-serious adverse events

When possible, the medical diagnosis should be reported as the Event Term instead of individual symptoms.

If it is unclear whether or not an event fits one of the above categories, or if the event cannot be isolated from the device or procedure, it should be submitted as an adverse event and/or device deficiency.

Any AE reportable event, experienced by the study subject after informed consent a, whether prior to, during or subsequent to the procedure, must be recorded in the eCRF.

Underlying diseases and chronic conditions are not reported as AEs unless there is an increase in severity or frequency during the course of the investigation. Death should not be recorded as an AE, but should only be reflected as an outcome of one (1) specific SAE (see Table 17.2-1 for AE definitions).

Refer to Instructions for Use for the known risks associated with the commercial device(s).

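### Note 2 to the safety definitions leaves persisting effects of tested but discarded settings unreported and does not say that serious in-session events stay reportable

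*Combined protocol and SAP*

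**What the plan says.** The rule is item 2 of the NOTES that follow Table 17.2-1 in section 17.2 of the protocol. It has two sentences. The first is an exclusion: "Sensations or side effects that occur during the programming session should not be reported as AEs". The second opens with a however and restores reporting for those that are "caused by the final programming parameters (including active contact, pulse width, frequency, and amplitude) that persist or occur after the completion of the programming".

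Two other sections set what the study is meant to capture.

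- Section 17.1 lists what sites must report to the sponsor. The list includes "All Serious Adverse Events" and "Device-hardware, device-stimulation, and procedure related non-serious adverse events". Neither entry makes an exception for programming sessions. The same section says that when the category of an event is unclear, or the event cannot be separated from the device or procedure, "it should be submitted as an adverse event and/or device deficiency".
- Section 6.6 defines the safety outcome: "Safety parameters include the rates of occurrence of all device hardware, device stimulation and procedure related non-serious adverse events, all serious adverse events", together with unanticipated events, through the end of the study.

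**The concern.** A programming session is where contacts, pulse width, frequency and amplitude are tried and adjusted, so some stimulation-related effects will begin there, and some will come from settings that are not kept. The exclusion in Note 2 has no limit by seriousness, severity or duration. The restoring sentence depends on the final parameters being the cause. That leaves two places where a site following the note to the letter could act differently from a site following 17.1: an effect of a discarded setting that does not go away, and an in-session event that meets a seriousness criterion.

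Two things are at stake. The first is completeness of the rates in section 6.6. The study has a single arm, so no control group shares the same ascertainment, and an omitted event lowers an absolute rate directly. The second is prompt sponsor review. Table 17.4-1 gives sites 3 calendar days for a serious adverse device effect and 10 days for a serious adverse event. The sponsor's medical safety group (section 19.1) reviews events once sites have reported them.

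Programming is not a one-off. It runs from activation to the Programming Lock Visit (Day 70, less up to 7 days) and takes place again at the 6-Month Visit (section 10.12). Section 10.15 allows unscheduled programming visits without a limit on number.

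**Working it through.** The documents state no event rate on this point, so there is no figure to reproduce. The check is to take each kind of event and read it against Note 2 and against 6.6 and 17.1.

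1. **Non-serious, begins and ends within the session, any setting.** Note 2: not reported. This is the ordinary case the note appears to be written for.
2. **Non-serious, caused by the final settings, begins in the session and persists, or begins afterwards.** Note 2: reported, because such effects "that persist or occur after the completion of the programming should be reported as AEs". Sections 6.6 and 17.1: reported. The two agree.
3. **Non-serious, caused by a tested and discarded setting, begins in the session and persists.** Note 2, first sentence: excluded, because it occurred during the session. Second sentence: not restored, because the final parameters did not cause it. Sections 6.6 and 17.1: within scope as a stimulation-related non-serious event. **The two disagree.**
4. **Non-serious, caused by a discarded setting, first felt after the session.** Note 2 neither excludes nor names it, so 17.1 governs and it is reportable. The note could be clearer, but it does not remove the event.
5. **Occurs in the session and meets a seriousness criterion.** Note 2 says nothing about seriousness. Section 17.1 requires all such events. **The two are not reconciled**, and no order of precedence is visible.

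Three further readings bear on cases 3 and 5.

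- **Definitions.** Table 17.2-1 defines a serious adverse event as an adverse event with one of the listed outcomes. It defines an adverse device effect as an adverse event related to use of the device, and a serious adverse device effect as an adverse device effect with serious consequences. A site told that something is not to be reported as an AE could conclude that it cannot be either serious category.
- **Reporting channel.** Table 17.4-1 routes serious adverse events, serious adverse device effects and adverse device effects through the AE page of the eCRF. That is the page Note 2 tells the site not to use.
- **Neighbouring notes.** Item 3 excludes lack of efficacy but keeps clinical sequelae other than pain reportable. Item 5 excludes a bare device deficiency but keeps any AE it precipitates reportable. Item 2 has no matching provision for harm that follows from the excluded occurrence, except where the final parameters caused it. The adverse device effect definition covers events arising from operation of the device and does not separate final from tested settings.

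Direction of the effect: with a true rate of stimulation-related events R and a share s of them omitted under case 3, the reported rate is R × (1 − s). Since s lies between 0 and 1, this is never above R. The documents give neither R nor s.

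**The case against.** The strongest defence is that Note 2 is a sensible convention with a carve-out. Section 4.2 describes programming as trying combinations on the basis of patient feedback, so passing sensations from trial settings are part of the procedure and need not be counted as adverse events. That stands, and the fix keeps it.

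Four stronger readings are tempting, and the documents do not support them.

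- **That the note bars every side effect arising in a session.** It does not. An effect that starts in the session, is caused by the final settings and persists is expressly reportable.
- **That stimulation harms are lost.** This is not established. Section 17.1 and Table 17.4-1 require all serious adverse events without qualification. An injury falls within the AE definition, while the note speaks only of sensations and side effects. The definition of an unanticipated adverse device effect does not depend on the term AE, so the note does not by its terms remove such an event. A malfunction or use error in a session is a device deficiency, with its own form and a 3-calendar-day limit. The submit-if-unclear rule in 17.1 also points towards reporting.
- **That the note flatly contradicts 17.1.** It can be read as saying which expected in-session sensations count as AEs at all, leaving the duty for serious events intact. The accurate description is that the two are unreconciled.
- **That the under-count can be given a size.** A reader might assume a true rate of 15% and an omitted share of one third, giving 0.15 × (1 − 1/3) = 10%, or of one tenth, giving 0.15 × 0.9 = 13.5%. None of these inputs is in the documents, and the share could be close to zero. If the share counts every event that begins in a session from a setting not kept, it includes transient sensations that a corrected note would still leave out, so the difference would not measure this gap.

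What the defence does not answer is case 3, where the wording itself excludes a persisting effect, and the silence on seriousness in case 5. The submit-if-unclear rule helps only a site that sees a doubt; one that takes Note 2 as a direct instruction may see none.

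**Conclusion.** The point holds as a drafting gap with a consequence for a stated safety outcome. Followed literally, Note 2 omits non-serious effects of tested but discarded settings that outlast the session, which 6.6 and 17.1 call for. It also fails to say that events meeting a seriousness criterion remain reportable. Since serious events are defined as a type of AE and reported on the AE page, a site could wrongly withhold one. Any effect on the reported stimulation-related rate is downward, and its size cannot be estimated from the documents. The only visible hypothesis concerns effectiveness, so no hypothesis test is affected.

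This rests on two assumptions: that some sites apply Note 2 as written, and that no instruction in the redacted parts of the programming-visit sections already settles the matter. The correction is worth making because it is small and protects both the rates and the expedited reporting route.

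**What to change.** Reword item 2 of the NOTES in section 17.2 so that the exemption covers only transient, non-serious sensations that have resolved by the end of the session. Add that any event meeting a seriousness criterion, and any effect that persists or recurs after the session, is reported under 17.1, whether the parameters that caused it were final or only tested. Cover the change in site training.

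The cost is a short wording change, a few more AE forms, and a slightly higher reported rate of stimulation-related adverse events.

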***17.3. Relationship to Study Device(s) and /or study Procedure***

The Investigator must assess the relationship of the reportable AE to the study device-hardware, device-stimulation and/or study procedure. See criteria in Table 17.3-1:

**Table 17.3-1: Criteria for Assessing Relationship of Study Device Hardware, Device Stimulation or Procedure to Adverse Event**

Classification	Description

Not Related  Ref: MDCG 2020-10/1
	
Relationship to the device or procedures can be excluded when:
 
 
- the event has no temporal relationship with the use of the study device or the procedures related to the use of the study device;
 
- the serious event does not follow a known response pattern to the medical device (if the response pattern is previously known) and is biologically implausible;
 
- the discontinuation of medical device application or the reduction of the level of activation/exposure - when clinically feasible – and reintroduction of its use (or increase of the level of activation/exposure), do not impact on the serious event;
 
- the event involves a body-site or an organ that cannot be affected by the device or procedure;
 
- the serious event can be attributed to another cause (e.g. an underlying or concurrent illness/ clinical condition, an effect of another device, drug, treatment or other risk factors);
 
- the event does not depend on a false result given by the study device used for diagnosis, when applicable; - In order to establish the non-relatedness, not all the criteria listed above might be met at the same time, depending on the type of device/procedures and the serious event.
 

Possibly Related  Ref: MDCG 2020-10/1
	
The relationship with the use of the study device is weak but cannot be ruled out completely. Alternative causes are also possible (e.g. an underlying or concurrent illness/ clinical condition or/and an effect of another device, drug or treatment). Cases where relatedness cannot be assessed or no information has been obtained should also be classified as possible.

Probably Related  Ref: MDCG 2020-10/1
	
The relationship with the use of the study device, or comparator, or relationship with procedures seems relevant and/or the event cannot be reasonably explained by another cause.


Causal Relationship Ref: MDCG 2020-10/1
	
The serious event is associated with the study device or with procedures beyond reasonable doubt when:
 
 
- the event is a known side effect of the product category the device belongs to or of similar devices and procedures;
 
- the event has a temporal relationship with the study device use/application or procedures;
 
- the event involves a body-site or organ that             
 
-the study device or procedures are applied to;
 
-the study device or procedures have an effect on;
 
 
 
- the serious event follows a known response pattern to the medical device (if the response pattern is previously known);
 
- the discontinuation of medical device application (or reduction of the level of activation/exposure) and reintroduction of its use (or increase of the level of activation/exposure), impact on the serious event (when clinically feasible);
 
- other possible causes (e.g. an underlying or concurrent illness/ clinical condition or/and an effect of another device, drug or treatment) have been adequately ruled out;
 
- harm to the subject is due to error in use;
 
- the event depends on a false result given by the study device used for diagnosis, when applicable;
 
- In order to establish the relatedness, not all the criteria listed above might be met at the same time, depending on the type of device/procedures and the serious event.
 

-----------------------------------------------------------	-----------------------------------------------------------------------------------------------------------------------------------------------------------------------------------------------------------------------------------------------------------------------------------------------------------------------------------------------------------------------------------------------------------------------------------------------------------------------------------------------------------------------------------------------------------------------------------------------------------------------------------------------------------------------------------------------------------------------------------------------------------------------------------------------------------------------------------------------------------------------------------------------------------------------------------------------------------------------------------------------------------------------------------------------------------------------------------------------------------------------------------------------------------------------------------------------------------------------------------------------------------------------------------------------------------------------------------------------------------------------------------------------------------------------------------------------------------------------------------------------------------------------------------------------------------------------------

#### 17.4. Investigator Reporting Requirements

The communication requirements for reporting to BSC are as shown below.

**Table 17.4-1: Investigator Reporting Requirements**

Event Classification	Communication Method	Communication Timeline post-market studies* (EU MDR 2017/745, MDCG 2020-10/1 MEDDEV 2.12/2: GUIDELINES ON A MEDICAL DEVICE VIGILANCE SYSTEM)
Unanticipated Adverse Device Effect	Complete AE eCRF page with all available new and updated information.	
 
• Within 1 business day of first becoming aware of the event.
 
• Terminating at the end of the study.
 

	Provide all relevant source documentation (de-identified/ pseudonymized) for reported event.	
 
• Upon request of sponsor.
 

Serious Adverse Event	Complete AE eCRF page with all available new and updated information.	
 
• Within 10 days after becoming aware of the event or as per local/regional regulations.
 
• Reporting required through end of the study.
 

Event Classification	Communication Method	Communication Timeline post-market studies* (EU MDR 2017/745, MDCG 2020-10/1 MEDDEV 2.12/2: GUIDELINES ON A MEDICAL DEVICE VIGILANCE SYSTEM)
	Provide all relevant source documentation (de-identified/ pseudonymized) for reported event if requested by safety.	
 
When documentation is available
 

Serious Adverse Device Effects	Complete AE eCRF page with all available new and updated information.	
 
Within 3 calendar days of first becoming aware of the event or as per local/regional regulations.
 
Reporting required through the end of the study
 

	Provide all relevant source documentation (de-identified/ pseudonymized) for reported event.	
 
When documentation is available
 
Upon request of sponsor
 

Device Deficiencies (including but not limited to malfunctions, use errors, and inadequacy in information supplied by the manufacturer, including labelling) Note: Any Device Deficiency that might have led to a serious adverse event if appropriate action had not been taken or intervention had not occurred circumstances had been less fortunate is considered a reportable event.	Complete Device Deficiency eCRF with all available new and updated information.	
 
Within 3 calendar days of first becoming aware of the event. Reporting required through the end of the study
 

	Provide all relevant source documentation (de-identified/ pseudonymized) for reported event if requested by safety.	
 
At request of sponsor
 

Adverse Device Effects	Complete AE eCRF page, which contains such information as date of AE, treatment of AE resolution, assessment of seriousness and relationship to the device.	
 
In a timely manner but not later than 30 business days after becoming aware of the information
 
Reporting of Adverse events which are device hardware, device stimulation and procedure related will be required through the end of the study.
 

	Provide all relevant source documentation (de-identified/ pseudonymized) for reported event if requested by safety.	

### **17.5. Device Deficiencies**

Device deficiencies will be documented and reported to BSC. If possible, the device(s) under study should be returned to BSC for analysis. Instructions for returning the device(s) will be provided to study sites. Device deficiencies should also be documented in the subject's source records.

Device deficiencies are not adverse events. However, an adverse event that results from a device deficiency, would be recorded as an adverse event on the appropriate eCRF.

### **17.6. Reporting to Regulatory Authorities / IRBs / Investigators**

BSC is responsible for reporting adverse event information to all participating Principal Investigators, IRBs and regulatory authorities, as applicable.

The Principal Investigator is responsible for informing the IR and regulatory authorities of UADEs and SAEs as required by local/regional regulations.

## **18. Informed Consent**

Subject participation in this clinical study is voluntary. Informed Consent is required from each subject. The Investigator is responsible for ensuring that Informed Consent is obtained prior to the use of any study devices, study-required procedures and/or testing, or data collection.

The obtaining and documentation of Informed Consent must be in accordance with the principles of the Declaration of Helsinki, ISO 14155, any applicable national regulations, and local Ethics Committee and/or Regulatory authority, as applicable. The ICF must be accepted by BSC or its delegate (e.g. CRO), and approved by the site's IRB, or central IRB, if applicable.

Boston Scientific will provide a study-specific template of the ICF to investigators participating in this study. The ICF template may be modified to meet the requirements of the investigative site's IRB. Any modification requires acceptance from BSC prior to use of the form. The ICF must be in a language understandable to the subject and if needed, BSC will assist the site in obtaining a written consent translation. Privacy language shall be included in the body of the form or as a separate form as applicable.

The process of obtaining Informed Consent shall at a minimum include the following steps, as well as any other steps required by applicable laws, rules, regulations and guidelines:

- be conducted by the Principal Investigator or designee authorized to conduct the process,
- include a description of all aspects of the clinical study that are relevant to the subject's decision to participate throughout the clinical study,
- avoid any coercion of or undue influence of subjects to participate,
- not waive or appear to waive subject's legal rights,

- use native language that is non-technical and understandable to the subject or his/her legal representative,
- provide ample time for the subject to consider participation and ask questions if necessary,
- ensure important new information is provided to new and existing subjects throughout the clinical study.

The ICF shall always be signed and personally dated by the subject competent to sign the ICF under the applicable laws, rules, regulations and guidelines and by the investigator and/or an authorized designee responsible for conducting the informed consent process. The original signed ICF will be retained by the site and a copy of the signed and dated document and any other written information must be given to the person signing the form.

Failure to obtain subject consent will be reported by BSC to the applicable regulatory authority according to their requirements (e.g., FDA requirement is within 5 working days of learning of such an event). Any violations of the informed consent process must be reported as deviations to the sponsor and local regulatory authorities (e.g. IRB), as appropriate.

If new information becomes available that can significantly affect a subject's future health and medical care, that information shall be provided to the affected subject(s) in written form via a revised ICF or, in some situations, enrolled subjects may be requested to sign and date an addendum to the ICF. In addition to new significant information during a study, other situations may necessitate revision of the ICF, such as if there are amendments to the applicable laws, protocol, a change in Principal Investigator, administrative changes, or following annual review by the IRB. The new version of the ICF must be approved by the IRB. Acceptance by Boston Scientific is required if changes to the revised ICF are requested by the site's IRB. The IRB will determine the subject population to be re-consented.

